#### 14.1 PRIMARY EFFICACY ANALYSIS

## 14.1.1 Analysis Population and Estimand

The primary endpoints will be analyzed using a "composite strategy" (International Conference on Harmonization (ICH) guideline E9 addendum on estimands and sensitivity analysis in clinical trials to the guideline on statistical principles for clinical trials). The estimand is defined by the following:

- Population: adult recipients of a double pulmonary allograft with clinically defined BOS, matching the inclusion and exclusion protocol criteria.
- Variable: FEV1 data at Week 48 (visit 9) collected from the onsite CO spirometer (data collected with the CO home spirometer will be used for supplementary analyses).
   Only accepted over-reader best FEV1 data for the session from CO will be used for analysis; data will not be re-derived.

Final Version 5.0 Page 38 of 76

Intercurrent events: After IEs such as stopping treatment with L-CsA, augmentation of SoC therapy, etc.,  $FEV_1$  measurements will still be collected and used in the analysis. In case of IEs preventing the use of  $FEV_1$  measurements, i.e. death and re-transplantation, the  $FEV_1$  will be imputed as treatment failure:  $FEV_1$  equal to zero for all visits subsequent the event.

Rejected spirometries are those that did not meet the American Thoracic Society criteria; if rejected, then they would be re-done but there may be cases where they are rejected twice and resulting in missing data. Rejected spirometry is not an indicator of a better/worse outcome and can be assumed to be MAR.

• Population-level summary: difference in mean change from baseline in the FEV1 at week 48 between treatment groups.

Table 5 summarizes the statistical approaches for handling IEs and missing data.

Final Version 5.0 Page 39 of 76

Table 5: Summary of strategies for Intercurrent Events and Missing data.

	Statistical analysis					
Type of IEs	Primary analysis (section 14.1.3)	Missing data not at random (MNAR) (section 14.2.1)	"While on treatment" strategy (for COVID-19) (section 14.3.3.3)	"While on treatment" strategy (section 14.3.5)	Trimmed Means (section 14.3.6)	
Death	The FEV 1 value will be	The FEV 1 value will be imputed equal to zero.	Not applicable.	Not applicable.	The FEV 1 value will be	
Re-transplantation	imputed equal to zero.		The FEV 1 value will be imputed equal to zero.	The FEV 1 value will be imputed equal to zero.	imputed equal to zero at W48.	
Treatment discontinuation  Study discontinuation for lack of efficacy*		FEV 1 measurements after IE will still be collected and included in the	FEV 1 measurements after IE will still be collected and included in the analysis.	Data after IE will not be considered**.	FEV 1 measurements after IE will still be collected and included in the analysis. Last observation will be used for	
Initiation of additional immunosuppressive	FEV 1 measurements after IE will still be collected and included in the					
COVID-19 infection	analysis. analysis.		Data after IE will not be considered.	FEV 1 measurements after IE will still be collected and included in the analysis.	determining the ordering of patients to be trimmed.	
In case of: - residual missing data, or - study discontinuation for consent withdrawal or lost to follow-up:	Missing data handled under MAR	Missing data imputed using fully conditional specification based on data from retrieved discontinued patients ***.	Missing data handled under MAR	Missing data handled under MAR	Last observation will be used for determining the ordering of patients to be trimmed. Missing data handled under MAR.	

\* If a patient discontinues the study for lack of efficacy, he/she will be encouraged to complete the follow-up visits planned in the protocol. All patients who prematurely discontinue the study should complete at least the evaluation at EoT prior to discontinuation whenever possible.

\*\* Two analyses will be performed: first considering only treatment discontinuation as IEs, then considering the initiation of additional immunosuppressive too.

\*\*\* If there are not enough retrieved patients for the convergence of MI-RD regression model, a reference-based MI will be adopted.

### 14.1.2 Working Hypothesis

The alternative hypothesis  $(H_1)$  for this trial is that L-CsA plus SoC is superior to SoC alone in preserving FEV1, i.e., under  $H_1$  it is expected that patients treated with L-CsA plus SoC will exhibit a smaller mean FEV1 decline between baseline and the end of Week 48 than those who receive SoC alone.

### 14.1.3 Analysis Model

The primary efficacy analysis will be carried out using a LMM for repeated measurements, using all observed available  $FEV_1$  measurements. In case of death or re-transplantation events,  $FEV_1$  will be imputed as zero at each nominal day post event.

The dependent variables are the absolute change from baseline of FEV1 measurements at visit 2 (i.e., the first post-baseline visit) through visit 9 (Week 48). For the definition of baseline FEV1 please refer to section 8.1.1.

A flexible and robust model will be chosen for the random part of the LMM according to a prespecified stepwise procedure (see next section). The fixed part of the LMM is specified as follows: the model will contain (except from the intercept) time cubic splines, treatment, the interactions of time splines by treatment, baseline FEV1, the interactions of time splines with the baseline FEV1, region (North America versus all other countries together), age (< 55 versus  $\ge 55$  years), and use of azithromycin at randomization (i.e. Baseline, Visit 1).

The primary efficacy parameter will be estimated from the model by the adjusted difference between treatment groups in mean FEV1 change from baseline after 48 weeks. The p-value for the null hypothesis of no difference and a two-sided 95% confidence interval for the difference will be provided.

Superiority of L-CsA will be demonstrated by a statistically significant result (defined as p<0.025, one-sided) in favor of the L-CsA plus SoC treatment compared to SoC alone.

The above comparison between treatment groups at all the other visits (2-8) will also be presented.

A figure of observed mean change from baseline and standard errors at each visit, by treatment group will be presented. A figure with adjusted mean changes from baseline at each visit by treatment group derived from the LMM will be provided.

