#### 7.2 Randomization and Stratification

At the Baseline visit (V1), after all inclusion and exclusion criteria have been fully evaluated, eligible patients will be randomized with equal probability to one of two treatment arms, a control arm (SoC alone) and an investigational arm (L-CsA plus SoC). The investigational medicinal product (IMP) is L-CsA. To assure balance between treatment arms with regard to key variables and potential confounders, stratification prior to randomization will be performed for the following variables:

- Screening FEV1 ≥81% of personal best FEV1 value post-transplant versus Screening FEV1 between 80-51% of personal best FEV1 value post-transplant;
- Age at the time of randomization: <55 years versus ≥55 years;

- · Region: North America versus all other countries together.

Within each of the 8 strata, patients will be randomly assigned with equal probability (1:1) to either the investigational or control arm using a permuted blocks randomization. The randomization code, including specification of the block size, will be generated by a statistician not otherwise involved with the trial, using validated software. The unique randomization number and treatment assignment of each patient will be provided to the Investigator through the electronic Case Report Form (eCRF) after eligibility has been verified. The number assigned to a patient will be that patient's unique identifier throughout the clinical trial and cannot be re-assigned to another patient.

This is an open-label clinical trial. Clinical trial monitors, treating physicians, study nurses, study coordinators, and enrolled patients will not be blinded to treatment assignment.

[figure not shown]

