## 14.1.4 Specification of the Model

For valid inference on the primary efficacy parameter, the evolution of  $FEV_1$  in both treatment groups should be modeled as a flexible function in time, without unnecessarily strong assumptions.

Therefore, time will be modeled assuming that the time evolution of  $FEV_1$  is a smooth function of time. Cubic splines will be used with a large enough number of parameters to minimize the risk of misspecification. We will choose one knot at 182 days, i.e., halfway between the first (day 28) and

the last scheduled measurement (337 days). So, it is assumed that the mean of FEV1 is a third-degree polynomial at each of the two intervals, smoothly connected, equal at day 182 with equal first and second derivative. Thus, 4 parameters per group are used to model time. In total, as many as 12 parameters in the model will involve time, ensuring robust estimation of the time evolution of FEV1. Denoting the covariates associated with the splines by S1=t, S2=t, S3=t and S4=max(t-182,0), the treatment group by T (0=SoC; 1=L-CsA plus SoC), the day of the measurement by t and the baseline FEV1 by X, the fixed part of the model will contain the following covariates:

The Kenward-Roger adjustment will be used for the denominator degrees of freedom needed for hypothesis tests and confidence intervals.

The other covariates are:

- Age (< 55 versus ≥ 55 years);

- Region (North America versus all other countries together);
- Use of azithromycin at randomization.

In the unlikely case of collinearity, covariates will be dropped in the above order, starting with the last.

The random part of the LMM will be selected by comparing the Akaike Information Criterion (AIC) of three models:

- model with random intercept and random time;
- model with random intercept, random time and random squared time;
- model with random intercept, random time, random squared time, and random cubic time.

The model with the lowest AIC will be adopted for the primary analysis.

The core excerpt of cole code for the primary analysis is reported in section 17.1.

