### 14.2 Sensitivity Analyses for the Primary Endpoint

### 14.2.1 Missing data not at random (MNAR)

To investigate the impact of departures from MAR assumption, a MNAR approach will be evaluated using the LMM described for the primary analysis. After remapping of the visits as per section 9.4, FEV1 at specific visit will be imputed depending on the IE experienced by the patient.

In case of IEs as death or re-transplantation, FEV1 will be imputed as zero at each post-event nominal day as per section 9.4. Other IEs (see Table 5) will be addressed per treatment policy strategy, and FEV1 measurements collected after IE will be used in the analysis.

Residual missing data (or missing data due to discontinuation for consent withdrawal or patient lost to follow-up) will be imputed using fully conditional specification, a type of multiple imputation using chained equations, implemented with column under the FCS option. The imputation model will include baseline FEV1, age (as a continuous variable), region, use of azithromycin at randomization, and intermediate FEV1 up to week 48 as covariates. Two hundred data sets will be generated, and the random seed number will be 52082. In case of imputation, the associated nominal day of assessment will be considered as per section 9.4.

Only observed values from retrieved discontinued patients will be used to inform the MI regression model (this model will be defined as MI-RD). Retrieved discontinued patients are defined as patients who discontinue study treatment and decide to remain in the study by following the schedule of assessments and continuing to adhere to protocol requirements. If there are not enough retrieved patients for the convergence of MI-RD regression model, a reference-based MI will be adopted: imputation of values in the investigational arm will be done using the non-missing values from the control group (this approach will be referred as "Copy Reference"). This approach does not assume benefits for the investigational arm in case of discontinuation and limits a post-discontinuation clinical effect to that of SoC. The final decision on the use of the MI-RD vs Copy-Reference will be done at the time of the analysis and reported in the CSR.

Each of the 200 imputed datasets will be analyzed using the LMM (see primary analysis) including all observed and imputed data. Rubin's rule [2] will be used for combining results to draw inference.

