### 14.2.2 Delta-Based Controlled Imputation (Tipping point)

A delta-based controlled imputation approach using the tipping point analysis will be performed as a sensitivity analysis of treatment superiority, if shown. Tipping point analysis will assess how departures from MAR assumption must be to overturn conclusions from the primary superiority analysis. Tipping point will be based on iterative application of MI.

In case of death or re-transplantation events, FEV1 will be imputed as zero at each nominal day post event.

In the first iteration, the missing FEV1 outcomes will be imputed separately for each treatment group, using the fully conditional specification. The imputation model will include baseline FEV1, age, region, use of azithromycin at randomization, and intermediate FEV1 up to week 48 as covariates. Two hundred data sets will be generated, and the random seed number will be 99823. Non-missing values from all patients will be used.

In successive iterations, to represent departures from MAR, values  $\Delta 1$  and  $\Delta 2$  will be added and subtracted to the imputed values for L-CsA plus SoC treatment and SOC treatment groups respectively.  $\Delta 1$  and  $\Delta 2$  will range from 0 to 100 mL (0.1 L) by 10 mL (0.01 L).

For each scenario (i.e., each combination of  $\Delta 1$  and  $\Delta 2$ ), the 200 delta-adjusted imputed datasets will be analyzed using the primary LMM including all observed and imputed data. Rubin's rule will be used for combining results to draw inference. The adjusted difference between treatment groups in mean FEV1 change from baseline after 48 weeks will be provided along with its p-value for the null hypothesis of no difference.

These results will show how extreme the departures from MAR must be to overturn the results of the primary analysis. Controlled imputation is always feasible, independent from the incidence of dropouts.

The core excerpt of code for this sensitivity analysis is reported in section 17.3.

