## 14.2.3 Mixed model repeated measures (MMRM)

To investigate robustness against deviations from the model, a MMRM model will be carried out using all observed available FEV1 measurements (under MAR assumption). The dependent variables are the absolute change from baseline of FEV1 measurements at visit 2 (i.e., the first post-baseline visit) through visit 9 (Week 48). In case of death or re-transplantation events, FEV1 will be imputed as zero at each nominal day post event.

As fixed effects, the model will contain the following covariates (except from the intercept): categorical (scheduled) visit, treatment, the interactions of treatment by categorical visit, baseline  $FEV_1$ , the interactions of categorical visit with the baseline  $FEV_1$ , region (North America versus all other countries together), age (< 55 versus  $\geq$  55 years), and use of azithromycin at

Final Version 5.0 Page 44 of 76

randomization (i.e. Baseline, Visit 1). Random effects per patient for this model will include categorical visit.

An unstructured covariance pattern will be used to estimate the variance—covariance of the withinpatient repeated measures. If the model fails to converge, a heterogeneous Toeplitz structure will be used. Parameters will be estimated using REML with the Newton—Raphson algorithm and using the Kenward—Roger method for calculating the denominator degrees of freedom.

Treatment group comparisons at each visit will be estimated by differences between least squares (LS) means from the visit by treatment interaction, with accompanying p-values and 95% CIs. The robustness of primary results will be evaluated by means of the difference of LS means at week 48.

The core excerpt of code for the sensitivity analysis is reported in section 17.4.

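### The primary mixed model and its supporting models omit one of the three randomization strata (screening FEV1 as % of personal best); if it is prognostic, the reported SE is slightly too large, and recovering the loss needs stratum-by-time terms

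*SAP*

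**What the plan says.** SAP Section 7.2 gives the purpose of the stratification: "To assure balance between treatment arms with regard to key variables and potential confounders, stratification prior to randomization will be performed". The factors are screening FEV1 as a percentage of personal best, age and region, and "Within each of the 8 strata, patients will be randomly assigned with equal probability". Protocol Section 9.3 names the same three factors.

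The primary model in SAP Section 14.1.3 contains time splines, treatment, treatment by splines, absolute baseline FEV1, "the interactions of time splines with the baseline" FEV1, then "region (North America versus all other countries together), age", and azithromycin use at randomization, which is not a stratification factor. Section 14.1.4 lists the remaining covariates as age, region and azithromycin, and adds: "In the unlikely case of collinearity, covariates will be dropped in the above order, starting with the last".

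The supporting models follow the same pattern:

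- Section 14.2.1 imputes from baseline FEV1, "age (as a continuous variable), region, use of azithromycin at randomization, and intermediate" FEV1.
- Section 14.2.2 imputes from baseline FEV1, "age, region, use of azithromycin at randomization, and intermediate" FEV1.
- Section 14.2.3 opens its list with "As fixed effects, the model will contain the following covariates (except from the intercept): categorical (scheduled) visit, treatment" and goes on to baseline FEV1, region, age and azithromycin.
- The piecewise model (14.3.3.2) has the same covariates.
- The ANCOVA (14.2.5) refers back to the stratification factors of the mixed model, which names only two of the three.

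The protocol's model (Section 15.2.3.1) has the same omission, so the two documents agree. Percentage of personal best otherwise appears as a severity subgroup (SAP Section 14.6), with different cut-points and baseline instead of screening FEV1. The stratification factors are tabulated by arm (SAP Section 10).

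**The concern.** Stratified randomization forces the arms into balance on the FEV1 stratum. If the stratum predicts change in FEV1, that balance reduces the true sampling variance of the treatment difference. A model without the stratum does not know this: it leaves the between-stratum variation in the residual and reports a standard error that is too large.

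Absolute baseline FEV1 does not close the gap. A patient at 2.0 L is at 55% of a personal best of 3.64 L (2.0/3.64) and at 90% of a personal best of 2.22 L (2.0/2.22). The covariate value is the same, but the strata differ.

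What is at stake is efficiency and agreement between design and analysis. A positive result is not threatened.

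**Working it through.** **Inputs from the documents.** One-sided alpha 0.025 (SAP 14.1.3); difference 200 mL, SD 350 mL, 50 per arm, 110 planned, 169 randomized (SAP 8.2); permuted blocks in 8 strata (SAP 7.2); nominal visit days 29, 57, 85, 113, 169, 225, 281, 337 (SAP 9.4); knot at day 182 (SAP 14.1.4).

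**Assumed.** R², the share of residual Week 48 variance the stratum explains beyond the covariates already in the model, is not in the documents. The values 0, 2, 5 and 10% are used. The stratum split is also not given; 50/50 is used.

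**1. The plan's sample size.** n per arm = 2(1.960 + 0.842)² × 350²/200² = 48.1, so 49 by the normal approximation. Exact t-test power is 79.96% at 49 and 80.8% at 50, so the stated 50 reproduces. A total of 110 corresponds to about 9% withdrawal: 100/0.91 = 109.9.

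**2. Could missing text hide the stratum?** The covariate formula in 14.1.4 and the code in 17.1 are not visible. However, 14.1.4 counts 12 parameters involving time: 4 splines + 4 treatment-by-spline + 4 baseline-by-spline = 12. No stratum-by-time term fits, and the list of other covariates has no stratum main effect.

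**3. Size at a single time point.** SE(omitted)/SE(adjusted) = 1/√(1 − R²). Actual one-sided level when omitted = 1 − Φ(1.96/√(1 − R²)).

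| R² | SE ratio | Actual level |
|---|---|---|
| 2% | 1.010 | 0.0239 |
| 5% | 1.026 | 0.0222 |
| 10% | 1.054 | 0.0194 |

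**4. The SAP's spline model, by simulation.** There were 1,000 trials per row with 169 patients and REML, using the SAP fixed effects with a random intercept and slope. Week 48 SD was 350 mL (residual SD 120 mL, intercept SD 150 mL, the rest slope), with blocks of 4 and 20% completely random dropout. Entries are the mean Week 48 SE in mL.

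| Stratum effect | R² | Omitted | Main effect only | Main + spline terms |
|---|---|---|---|---|
| None | 0% | 57.1 | 57.1 | 57.2 |
| On rate of decline | 2% | 57.1 | 57.0 | 56.6 |
| On rate of decline | 5% | 57.1 | 56.9 | 55.8 |
| On rate of decline | 10% | 57.1 | 56.6 | 54.3 |
| Constant shift | 5% | 57.1 | 55.8 | 55.9 |
| Constant shift | 10% | 57.1 | 54.4 | 54.5 |

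Before rounding, for an effect on the rate of decline, a main effect lowers the SE by 0.15%, 0.4% and 0.85%. The spline version lowers it by 0.9%, 2.4% and 4.9%. For a constant shift at R² of 5% and 10%, the falls are 2.2% and 4.6% (main effect) and 2.2% and 4.5% (splines). With no stratum effect, the spline version costs about 0.05%.

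A second simulation (500 trials, 15% dropout, R² 10%, effect growing with time) gave SEs of 56.3, 55.9 and 53.6 mL. The observed spread of the estimates was about 54 mL under all three models. A main effect recovered (56.34 − 55.89)/(56.34 − 53.59) = 16% of the fall that the spline terms achieved.

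**5. Power at 200 mL, N = 169** (normal approximation). SE(omitted) = 350 × √(4/169) = 53.85 mL; the true SE is 53.85√(1 − R²). Omitted: Φ((200 − 1.96 × 53.85)/true SE). Adjusted: Φ(200/true SE − 1.96).

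| R² | Omitted | Adjusted |
|---|---|---|
| 2% | 96.2% | 96.3% |
| 5% | 96.4% | 96.8% |
| 10% | 96.8% | 97.5% |

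**The case against.** The strongest reply is that this is too small to justify reopening the primary model. The omission errs on the safe side, and the power cost is under one point.

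The upper R² values also ask a lot. With a 50/50 split, R² = d²/(4 × 350²), so R² of 2, 5 and 10% needs a between-stratum difference d of about 99, 157 and 221 mL in Week 48 change. That is beyond what baseline FEV1 already explains, and the last exceeds the 200 mL treatment effect. Real precision is not lost either, because the spread of the estimates is the same under all three models. These points stand and limit the size of the finding. They do not remove it.

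The simulations use the simplest of the SAP's candidate random structures and leave out the zero imputation for death and re-transplantation. This makes the percentages uncertain but leaves the direction unchanged.

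Age and region are strata too and enter as main effects only, so giving time interactions to one stratum looks uneven. That is fair, but leaving those two as they are does no harm.

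An extra term in the imputation based on retrieved discontinued patients could make convergence harder, and Section 14.2.1 then switches method. This is a real cost, though it is one term, and it keeps the imputation model in line with the analysis model.

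Finally, protocol and SAP agree, and the trial is open-label and fully randomized. That is a reason to make the change before any comparative result is seen.

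**Conclusion.** The point holds as a worthwhile improvement, not an essential correction. The trial balances on three factors and adjusts for two, without a visible reason. If the third is prognostic beyond baseline FEV1, the Week 48 standard error is overstated by roughly 1 to 5% for R² of 2 to 10%, and the test is conservative by the amounts in step 3. There is no bias and no inflation of type I error. If R² is zero, nothing is lost.

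The omission is certain from the written covariate lists. Its size rests on the assumed R², equal strata, random dropout and the simplified random part. The need for stratum-by-time terms rests on a stratum effect that grows over follow-up, which is natural for a marker of decline but is assumed. Under a constant shift, a main effect would be enough. The spline version performs well in both cases.

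**What to change.** Before database lock and before any comparative result is viewed, add the as-randomized screening FEV1 stratum:

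- **Primary mixed model and the sensitivity analyses that use it:** main effect plus interactions with the four spline terms, as for baseline FEV1 (5 parameters).
- **MMRM:** main effect plus visit interaction (1 + 7 = 8 parameters).
- **Piecewise model:** main effect plus its two time interactions (3 parameters).
- **ANCOVA and both imputation models:** main effect (1 parameter each). Section 14.2.5 should name all three strata.

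Keep absolute baseline FEV1 and its time interactions. In Section 14.1.4, list the stratum ahead of azithromycin, so that azithromycin is still dropped first under collinearity.

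The cost is text and code edits in these sections, with no new data. Because the protocol's model also lacks the stratum, record the addition in SAP Section 16; protocol Section 15 makes the final SAP the analysis of record. If the sponsor prefers to leave the stratum out, one sentence of reason in the SAP would close the gap.
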